3.2.1.3 Ambulatory Blood Pressure

24-hour ambulatory blood pressure monitoring (ABPM) will be performed at timepoints as specified in the SoA in [Appendix A](#). During ABPM, systolic blood pressure (SBP), diastolic BP (DBP), heart rate (HR), and mean arterial pressure readings will be recorded over a period of 24 hours.

3.2.1.4 AZD5718 Plasma Concentrations

Venous blood samples will be collected for the measurement of plasma concentrations of AZD5718 as specified in the SoA in [Appendix A](#). The actual date and time (24-hour clock time) of each sample and date and time (24-hour clock time) of previous dose taken will be recorded in the eCRF. Site may refer to e-Diary or home dosing diary for time of last dose taken by the participant prior to dosing in clinic, if available.

A sub-group of at least 80 participants (20 per dose group including placebo) will have four additional PK samples taken within 1-2 hours (h), 2-5 h, 5-8 h, and 8-12 h post-dose (one sample taken at each time window with the additional requirement of at least 1 h between 2 subsequent samples) for analysis of AZD5718. As indicated in the SoA in [Appendix A](#), the additional samples will be taken at Visit 5 for only the sub-group of 80 participants, while pre-dose PK samples for analysis of AZD5718 will be collected from all study participants.

Samples for determination of AZD5718 (and dapagliflozin) concentration in plasma will be assayed by bioanalytical test sites operated by or on behalf of AstraZeneca, using an appropriately validated bioanalytical method. Full details of the analytical method used will be described in a separate Bioanalytical Report.

Drug concentration information that may unblind the study will not be reported to investigative sites or blinded personnel until the study has been unblinded.

3.2.2 Safety Variables

Safety will be assessed by descriptive analysis of adverse events (AEs) (including serious adverse events [SAEs]), vital signs, laboratory assessments, ECGs, and physical examinations.

3.2.2.1 Adverse Events/Serious Adverse Events

Adverse events are collected from time of first dose through to the Follow-Up Period. Serious adverse events will be collected from the time of signed informed consent through to the Follow-up Period.

3.2.2.2 Vital Signs

Vital signs will be performed at timepoints as specified in the SoA in [Appendix A](#). Vital signs will include BP, HR, respiratory rate, pulse oximetry, and body temperature. Vital signs should be collected pre-dose on the days of study drug dosing and before blood draws.

3.2.2.3 Clinical Laboratory Parameters (Clinical Chemistry, Haematology, and Urinalysis)

Blood and urine samples for determination of clinical chemistry, haematology, coagulation, and urinalysis will be taken at the visits indicated in the SoA in [Appendix A](#). Additional safety samples may be collected if clinically indicated at the discretion of the Investigator. The date, time of collection and results (values, units, and reference ranges) will be recorded on the appropriate eCRF. Clinical chemistry, haematology, and urinalysis will be performed at the central laboratory, except for the pregnancy test at Visit 3 which will be done locally via urine dipstick. Any other tests performed by urine dipstick are also performed locally, shown in [Table 1](#). The laboratory variables to be measured are presented in [Table 1](#).

Table 1 Laboratory Safety Variables

Haematology/Haemostasis (whole blood)	Clinical Chemistry (serum or plasma)
B-White blood cell count	S/P-Sodium
B-Red blood cell count	S/P-Potassium
B-Haemoglobin	S/P-Urea
B-Haematocrit	S/P-Creatinine
B-Mean corpuscular volume	S/P-Creatine kinase
B-Mean corpuscular haemoglobin	S/P-Albumin
B-Mean corpuscular haemoglobin concentration	S/P-Calcium
B-Neutrophils absolute count	S/P-Phosphate
B-Lymphocytes absolute count	S/P-Glucose (fasting) (Non-fasting at Screening Visit 1)
B-Monocytes absolute count	S/P-Alkaline phosphatase
B-Eosinophils absolute count	S/P-Alanine aminotransferase
B-Basophils absolute count	S/P-Aspartate aminotransferase
B-Platelets	S/P-Total bilirubin
B-Reticulocytes absolute count	S/P-Follicle stimulating hormone [^]
	S/P-Luteinising hormone [^]
Coagulation	S/P-Thyroid stimulating hormone
B-International normalised ratio	S/P-Free triiodothyronine
B-Activated partial thromboplastin time	S/P-Creatinine (for eGFR quantification)
B-Fibrinogen	S/P-Chloride
	S/P-Bicarbonate
Urinalysis *	S/P-Magnesium
U-Glucose (dipstick)	S/P-Human chorionic gonadotropin hormone [#]
U-Albumin (quantification/semi-quantification)	S/P-Albumin
U-Glucose	S/P-Total Protein
U-Blood (dipstick)	
U-White blood cells	
U-human chorionic gonadotropin hormone [@]	
Other Clinical Safety Panels[^] (serum or plasma)	
S/P-Hepatitis B surface Antigen (HBsAg)	
S/P-Hepatitis C virus antibody	

NB. In case a participant shows an AST or ALT $\geq 3 \times$ ULN together with total bilirubin $\geq 2 \times$ ULN, refer to Appendix E in the CSP.

* If urinalysis abnormal Microscopy through central laboratory – including white blood cells, red blood cells, and casts.

[^] Screening Visit 1 only.

[@] Via urine dipsticks.

3.2.2.4 Electrocardiogram Assessments

Triplicate 12-lead ECGs will be performed at timepoints as specified in the SoA in [Appendix A](#). The Investigator will make an overall evaluation of the ECG as normal or abnormal. If abnormal, it will be decided whether or not the abnormality is clinically significant or not clinically significant and the reason for the abnormality will be recorded on the eCRF.

3.2.2.5 Physical Examinations

Physical examination will be performed at timepoints as specified in the SoA in [Appendix A](#) and will include:

- A complete physical examination will be performed and include assessments of the following: general appearance, respiratory, cardiovascular, abdomen, skin, head and neck (including ears, eyes, nose and throat), lymph nodes, thyroid, muscular-skeletal (including spine and extremities) and neurological systems. Weight and body mass index (BMI) will also be collected.

- A brief physical examination will include, at a minimum, assessments of the skin, lungs, cardiovascular system, and abdomen (liver and spleen).

Any new or aggravated clinically relevant abnormal medical finding at a physical examination as compared with the baseline assessment will be reported as an AE unless unequivocally related to the disease under study.

CCI

CCI

4 STATISTICAL METHODS

4.1 Data Quality Assurance

All tables, figures and data listings to be included in the report will be independently checked for consistency, integrity and in accordance with standard Parexel procedures.

4.2 General Presentation Considerations

All efficacy and safety variables will be summarised by study treatment group using descriptive statistics. For continuous variables, descriptive statistics will include the number of participants (n), mean, SD, median, minimum and maximum. For log-normal variables, descriptive statistics will include n, mean, SD, median, minimum, maximum, geometric mean (GeoMean), and coefficient of variation (CV). Categorical variables will be summarised using frequencies and percentages. Continuous data that are expected to be skewed will be presented in terms of the maximum, upper quartile, median, lower quartile, minimum and number of observations. The minimum and maximum will be reported to the same number of decimal places as the raw data recorded in the database. The mean, median, lower quartile, and upper quartile will be reported to one more decimal place than the raw data recorded in the database. The SD will be reported to two more decimal places than the raw data recorded in the database. In general, the maximum number of decimal places reported shall be four for any summary statistic.

Percentages will be presented to one decimal place. Percentages will not be presented for zero counts. Percentages will be calculated using n as the denominator, unless otherwise specified. If sample sizes are small, the data displays will show the percentages, but any textual report will describe frequencies only.

Changes from baseline in categorical data will be summarised using shift tables where appropriate. P-values greater than or equal to 0.001, in general, will be presented to three decimal places. P-values less than 0.001 will be presented as “<0.001”.

Confidence intervals (CIs) will be presented to one more decimal place than the raw data.

Data will be summarised by-visit as applicable.

‘Baseline’ is defined as the last value obtained prior to the first dose of study medication, unless otherwise stated. ‘End of Study’ is defined as the last available post-treatment assessment. ‘Study Day’ will be calculated relative to the date of randomisation, ie:

If Assessment Date < Randomisation Date, then

$$\text{Study Day} = \text{Assessment Date} - \text{Randomisation Date}$$

If Assessment Date ≥ Randomisation Date then

$$\text{Study Day} = \text{Assessment Date} - \text{Randomisation Date} + 1$$

All visit-based summaries will use analysis visits. All post-randomisation scheduled and unscheduled visits (excluding Discontinuation Visit), will be mapped to an appropriate analysis visit as shown in [Table 2](#).

Table 2 Analysis Visit Windows

eCRF Visit	Target Day	Protocol Visit Window	Actual assessment day	Analysis visit
Visit 3 (randomisation)	D1	D1	D1	Randomisation
Visit 4 (Wk 2)	D15	D12 to D18	D2 to D21	Week 2
Visit 5 (Wk 4)	D29	D26 to D32	D22 to D42	Week 4
Visit 6 (Wk 8)	D57	D54 to D60	D43 to D71	Week 8
Visit 7 (Wk 12)	D85	D82 to D88	D72 to D88	Week 12
Visit 8 (Wk 16)	D113	D110 to D116	D89 to D127	Week 16
Visit 9 (Wk 20)	D141	D138 to D144	D128 to D144	Week 20
Visit 10 (Wk 24)	D169	D164 to D174	D145 to D183	Follow-up

Abbreviations: D = day; eCRF = electronic Case Report Form; Wk = week.

For visit-based summaries, if there is more than one value per participant within a time window, then the closest value will be summarised, or the earliest in the event the values are equidistant from the nominal visit date. The listings will highlight the value for that participant that went into the summary table, wherever feasible.

The Coronavirus Disease of 2019 (COVID-19) pandemic was declared by the World Health Organisation on 11 March 2020. Due to this, some COVID-19 specific summaries will be presented to summarise the impact of the pandemic.

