5.1 Inclusion Criteria

Participants are eligible to be included in the study only if all of the following criteria apply:

Age

- 1 Participants must be ≥ 18 years of age inclusive, at the time of signing the informed consent.

For participants who haven't reached the age of maturity according to local regulations in their country, a written informed consent should be obtained from the participant and his or her legally acceptable representative.

Type of Participant and Disease Characteristics

- 2 Participants with proteinuric CKD defined as
 - eGFR 20 – 75 mL/min/1.73m² based on chronic kidney disease epidemiology collaboration (CKD-EPI) equation at Screening Visit 1 **and**
 - albuminuria defined as 200 -5000 mg albumin/g creatinine based on the geometric mean of the replicated measurements using 3 sequential first morning void urine at Visit 2.**and**
 - with diagnosis of T2DM (for **DKD sub-group only**).

Weight

- 3 Body weight within 50-150 kg and BMI within the range 18 to 45 kg/m² (inclusive).

Sex

- 4 Male or female
- 5 Female participants must be of non-childbearing potential and must have been surgically sterilised (ie, bilateral oophorectomy, and/or complete hysterectomy, and/or bilateral salpingectomy; tubal ligation is not sufficient) or be postmenopausal (amenorrhoeic for 12 months or more following cessation of exogenous hormonal treatments and assessed by serum follicle stimulating hormone [FSH] and luteinising hormone [LH] levels at Screening Visit 1). All female participants must have a negative serum pregnancy test at Screening Visit 1 and negative urine pregnancy test at Visit 3 (Day 1) prior to study drug administration.
- 6 Male participants must be surgically sterile or agree to use highly effective contraceptives. Non-sterilised male participants who are sexually active with a female partner of childbearing potential must use a male condom with spermicide from Day 1 to 3 months after the last dose of the study drug. It is strongly recommended for the female partner of a male participant to also use a highly effective method of contraception throughout this period.

Note: In case a male condom with spermicide is not available in a country or region, non-sterilised male participants who are sexually active with a female partner of childbearing potential must use a male condom without spermicide and the female partner should use a highly effective contraceptive method.

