3.2.1 Efficacy Variables

3.2.1.1 Urine ACR

Urine ACR is a key marker for assessing kidney damage. Urine ACR is a ratio between measured albumin and measured creatinine, which estimates 24-hour urine albumin excretion. See the SoA in [Appendix A](#) for timing of collection.

Urine ACR will be calculated as:

$$\text{Urine ACR (mg/g)} = \frac{\text{urine albumin (mg/dL)}}{\text{urine creatinine (g/dL)}}$$

Spot urine samples are collected during the Screening Visit and at the remaining timepoints, participants are required to collect first morning void urine samples on 3 consecutive days. At each visit, the geometric mean of the triplicate ACRs will be computed centrally and used for all analysis of urine ACR.

Baseline urine ACR is taken to be the geometric mean of urine ACR geometric mean measurements taken at Visit 2 (Screening Visit 2) and Visit 3 (Study Day 1).

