3.2.1.2 Estimated GFR

Estimated GFR is a marker for assessing kidney function. Estimated GFR is calculated based on serum creatinine values and will be calculated by the central laboratory using the CKD-EPI equation as follows:

$$\begin{aligned} eGFR \text{ (mL/min/1.73m}^2\text{)} \\ &= 141 \times \min(SCr/\kappa, 1)^\alpha \times \max(SCr/\kappa, 1)^{-0.209} \times 0.993 \text{ Age} \\ &\times (1.018 \text{ if female}) \times (1.159 \text{ if Black}) \end{aligned}$$

Where SCr = serum creatinine (in mg/dL), κ is 0.7 for females and 0.9 for males, α is -0.329 for females and -0.411 for males, min indicates the minimum of SCr/ κ or 1, and max indicates the maximum of SCr/ κ or 1.

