4.9.3.2 Estimated GFR

Estimated GFR will be analysed, comparing eGFR at baseline with that at 12 weeks, to determine whether there is any acute change with the introduction of AZD5718 to inform planning for a GFR slope analysis in Phase 3. This will be analysed using a by-visit ANCOVA, adjusting for DM stratification factor, treatment group and baseline eGFR. The FAS will be used for this analysis and eGFR will be evaluated on the original scale. The analysis will be repeated on the Per-Protocol Analysis Population.

The results of the by-visit ANCOVA will be presented by treatment group. A summary of change from baseline of eGFR results will be presented by treatment group and a by-participant listing provided of eGFR results at each visit. Plots of the least-squares mean by treatment group over time, and the mean eGFR over time up to follow-up visit will be presented.

An ANCOVA model will be produced for eGFR up to Week 20, analysed on the Per-Protocol Analysis set, similarly to that described above.

The analysis will also be repeated by strata (DKD without SGLT2i background, DKD with SGLT2i background, non-DKD), adjusting for treatment group and baseline eGFR.

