Appendix A: Schedule of Activities

Table 6 Schedule of Activities

Study Period	Screening		Treatment Period 1				Treatment Period 2			Discontinuation	Follow-up
	1	2	3	4	5	6	7	8	9		10
Visit Number											
Study Day	-32 to -3		1	15±3	29±3	57±3	85±3	113±3	141±3		169±5
Study Week	-4 to 0		1	2	4	8	12	16	20		24
Informed consent (main)	X										
Informed consent (optional) for genetic and biomarker research	X										
Verify eligibility criteria	X	X	X				X ^a				
Demography	X										
Full physical examination including height, weight and BMI	X ^b		X		X		X		X	X	X
Physical examination (abbreviated)				X		X					
Medical history	X										
Serum hCG, FSH and LH ^e	X										
Pregnancy test ^c			X								
Drug and alcohol screen	X										
Hepatitis B and C screening	X										
Spot urine for ACR	X										
Safety laboratory assessments (Clinical chemistry, haematology, coagulation, urinalysis) ^d	X		X ^e	X	X	X	X	X	X ^e	X ^e	X
12-lead ECG	X		X	X	X	X	X	X	X	X	X
Vital signs ^f	X		X	X	X	X	X	X	X	X	X
Randomisation			X								
Retinal study (optional DKD sub-group only) ^g	X						X				
HbA1c ^h	X								X		
Calculation of eGFR	X		X	X	X	X	X	X	X	X	X
Blood sample for cystatin-C	X		X	X	X	X	X	X	X	X	X

Parexel International

AstraZeneca

Statistical Analysis Plan

Study Period	Screening		Treatment Period 1				Treatment Period 2			Discontinuation	Follow-up
	1	2	3	4	5	6	7	8	9		10
Visit Number	1	2	3	4	5	6	7	8	9		10
Study Day	-32 to -3		1	15±3	29±3	57±3	85±3	113±3	141±3		169±5
Study Week	-4 to 0		1	2	4	8	12	16	20		24
Pharmacokinetics plasma sample for AZD5718				X (pre-dose)	X ⁱ (pre-dose)	X (pre-dose)	X (pre-dose)	X (pre-dose)	X (pre-dose)	X (pre-dose)	
Pharmacokinetics plasma sample for dapagliflozin								X (pre-dose)	X (pre-dose)		
CCI [REDACTED]		X	X		X		X		X		
CCI [REDACTED]			X		X		X	X	X	X	
Plasma, serum, and urine for future use (optional) ^{j, h}			X		X		X		X	X	
Blood sample for genomic initiative (optional) ^j			X								
Dispense supply of containers for urine samples	X	X	X	X	X	X	X	X	X		
E-Diary, dispensation and completion of diary ^k			X	X	X	X	X	X	X	X	X
Reminder to collect first morning void urine samples, 3 days before visit ^l	X	X	X	X	X	X	X	X	X	X	
Urine samples for ACR ^{h, m}		X	X	X	X	X	X	X	X	X	X
24-hour ABPM, provision and completion		X ⁿ	X ^o			X ⁿ	X ^o				
Study drug dispensation ^p			X		X	X	X	X			
Study drug returned ^{p, q, r}					X	X	X	X	X	X	
Study drug intake in study centre			X	X	X	X	X	X	X	X	
Assessment of AEs/SAEs	Only SAEs		X	X	X	X	X	X	X	X	X

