Concomitant medications	X	X	X	X	X	X	X	X	X	X	X

- a Any participant with urine ACR < 30 mg/g at Week 12 will be excluded from Treatment Period 2. The eligibility check to enter Treatment Period 2 will be done at Visit 7 (Week 12) using the last available urine ACR result, calculated as the geometric mean of the replicated measurements using 3 sequential first morning urine voids.
- b Full physical examination will be completed at the indicated visits, with the exception that height will only be recorded at Screening Visit 1.
- c Serum hCG, FSH, and LH tests, and a urine dipstick pregnancy test are required for all women.
- d Except for Screening Visit 1, participants should be requested to be in a fasting state (except water) for at least 8 hours prior to sample collection and samples should be collected in the morning.

Parexel International

AstraZeneca

Statistical Analysis Plan

- e To include thyroid function tests (TSH, fT4 and fT3).
- f All vital signs (blood pressure, heart rate, respiratory rate, body temperature and pulse oximetry) will be measured with the participant in a supine position having rested for at least 10 minutes before each reading and should be taken before any blood draws. Vital signs should be collected pre-dose on the days of study drug dosing.
- g Optional, to be conducted only at study centres with the appropriate facility to conduct the assessment. There is no requirement for all participants at centres undertaking the sub-study to participate.
- h To be collected prior to study drug administration.
- h Containers to be dispensed at any study visit as required.
- i At specific PK sampling sites, for a sub-group of at least 80 participants (20 per dose group including placebo), 4 additional PK samples will be collected at this visit within 1-2 h, 2-5 h, 5-8 h, and 8-12 h post-dose. Pre-dose samples will be collected for all participants. Each PK sample must be separated by at least 1 h.
- j Only if consent is obtained. The blood sample for Genomic Initiative will be obtained from the participants at Visit 3 prior to study drug administration (at or after randomisation). If for any reason the sample is not drawn at Visit 3, it may be taken at any visit window until the last study visit. Only 1 sample should be collected per participant.

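### The eGFR analysis adjusts for one pre-dose value and leaves the Screening Visit 1 eGFR unused; adding it as a second covariate is a free, modest gain in precision

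*SAP*

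**What the plan says.** SAP 4.2 sets the general rule: baseline "is defined as the last value obtained prior to the first dose of study medication, unless otherwise stated". Neither SAP 3.2.1.2 and 4.9.3.2 nor protocol 8.1.2.1 and 9.4.2.2 states a different baseline for eGFR, so the rule applies. Baseline eGFR is one value, normally the Visit 3 (Day 1) value if it is drawn before dosing.

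The model in SAP 4.9.3.2 is: "This will be analysed using a by-visit ANCOVA, adjusting for DM stratification factor, treatment group and baseline eGFR". It has one eGFR covariate.

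The row "Calculation of eGFR" in SAP Appendix A is marked at Screening Visit 1 and at Visit 3, but not at Visit 2. Protocol Table 1 agrees. Both values come from the same source: "Estimated GFR is calculated based on serum creatinine values and will be calculated by the central laboratory using the CKD-EPI equation as follows".

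For urine ACR the SAP combines two pre-treatment visits: "Baseline urine ACR is taken to be the geometric mean of urine ACR geometric mean measurements taken at Visit 2" and at Visit 3 (SAP 3.2.1.1).

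**The concern.** Two eGFR readings exist before randomisation, and the model uses only the later one. A single creatinine-based reading contains short-term variation. A second reading of the same quantity usually explains some of the Week 12 variation that the first leaves over. If so, the standard error of each dose-placebo difference is larger than the collected data require.

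The comparison is a listed secondary objective. SAP 4.9.3.2 says that it is meant to show any acute eGFR change and to inform the Phase 3 slope analysis. SAP 4.14 reports 613 randomised and 340 completing treatment, and cautions that the efficacy analyses lack power. Precision that costs no further data is worth having in that setting.

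**Working it through.** **Plan's own figure.** There is none to reproduce. The documents state no SD, correlation, power or precision target for eGFR, and the sample size is built on urine ACR. Every correlation and SD below is an assumption.

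**Notation.** Let a be the correlation of Visit 3 with Week 12, b that of Screening Visit 1 with Week 12, and c that of Screening Visit 1 with Visit 3. Outcome variance is scaled to 1.

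- Residual variance, Visit 3 only: 1 - a².
- Residual variance, both as covariates: 1 - (a² + b² - 2abc)/(1 - c²).
- Residual variance, simple mean as the only covariate: 1 - ((a + b)/2)²/((1 + c)/2).
- SE ratio against the plan: square root of the variance ratio.

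**Step 1: all correlations equal (a = b = c = r).** The variance ratio reduces to (1 + 2r)/(1 + r)², and mean and two-covariate forms coincide.

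| r | Visit 3 only | Both | Ratio | SE reduction |
|---|---|---|---|---|
| 0.80 | 0.360 | 0.289 | 2.6/3.24 = 0.802 | 10.4% |
| 0.90 | 0.190 | 0.147 | 2.8/3.61 = 0.776 | 11.9% |
| 0.95 | 0.098 | 0.074 | 2.9/3.8025 = 0.763 | 12.7% |

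**Step 2: screening less correlated with Week 12 (a = c = 0.90).** Visit 3 alone leaves 1 - 0.81 = 0.190.

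- b = 0.88: R² = (0.81 + 0.7744 - 1.4256)/0.19 = 0.836. The residual is 0.164, a ratio of 0.864, and the SE falls 7.0%.
- b = 0.85: R² = (0.81 + 0.7225 - 1.377)/0.19 = 0.818. The residual is 0.182, a ratio of 0.956, and the SE falls 2.2%. The simple mean leaves 1 - 0.7656/0.95 = 0.194, so its SE **rises** 1.1%.
- b = 0.81 (= a × c, first-order decay): R² = (0.81 + 0.6561 - 1.3122)/0.19 = 0.81. The residual is 0.190, so there is no gain. The simple mean leaves 1 - 0.7310/0.95 = 0.2305, and its SE **rises** 10.1%.

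**Step 3: eligibility truncation and noisier screening samples.** This is a simulation with Screening Visit 1 eGFR restricted to 20-75. Assumptions: true eGFR mean 45 and SD 16, within-person SD 3 to 6, SD of true change 3.

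| Screening noise SD relative to Day 1 | SE reduction, both as covariates | SE reduction, simple mean |
|---|---|---|
| 1.0 | 8.1-9.2% | 8.1-9.2% |
| 1.3 | 5.9-6.4% | 5.2-5.5% |
| 1.6 | 4.2-4.6% | 1.1-1.6% |

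For scale, take 142 per group and within-person SD 4. The SE of a two-group difference goes from 0.747 to 0.679 mL/min/1.73m² with equal noise, and from 0.748 to 0.713 with 1.6-fold noise.

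**The case against.** **The plan is not in error.** Using the last pre-dose value as baseline, with ANCOVA on it, is valid under randomisation, and no stated eGFR precision target is missed. This stands, and it limits the point to efficiency.

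**Noise does not pass straight into the estimate.** A reader might infer that the single-reading noise carries over in full to the acute-change estimate. That describes an unadjusted change score. The ANCOVA already damps baseline noise and loses only some explained variance. The descriptive change-from-baseline summaries would be unaffected by the fix.

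**Screening Visit 1 is a poorer measurement than Visit 3.** It may fall up to 32 days before Day 1. It is the eligibility value, required to be 20-75 mL/min/1.73m² "based on chronic kidney disease epidemiology collaboration (CKD-EPI) equation at Screening Visit 1". It may be retested once. It is also exempt from the fasting request: "Except for Screening Visit 1, participants should be requested to be in a fasting state (except water) for at least 8 hours". These features stand as reasons to expect less than the equal-correlation gain. They are not reasons for bias: the selection precedes randomisation and is the same in every arm.

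**The urine ACR baseline is not a precedent for averaging.** Visits 2 and 3 use the same triplicate first-morning collection, whereas the two eGFR samples are taken under different conditions. A reader might call the two baseline rules inconsistent; the documents do not support that.

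**Timing and relevance.** The study stopped for lack of efficacy, which weakens the Phase 3 rationale. eGFR was also summarised in the unblinded interim, so a later covariate change needs a record. SAP 4.12.1 says that the main study team stayed blinded for the final analysis, so the change could still be specified without knowledge of results by arm.

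**Conclusion.** The point holds as a free improvement of low severity. One pre-dose eGFR is used, and a second central-laboratory value collected before randomisation is not. Entering both cannot bias the randomised comparison. In large samples it cannot lose precision; the finite-sample cost is one degree of freedom.

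The most reasonable expectation is an SE about 4-9% lower, under the assumptions of Step 3. The 10-13% figure is a best case that needs equal correlations of 0.80-0.95, and it should not be quoted alone. With correlations of 0.90, 0.85 and 0.90 the gain is about 2%, and with first-order decay it is zero. The documents do not say which case applies.

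They do not support a claim that the planned eGFR result would be biased or invalid, or that its precision is inadequate.

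**What to change.** In SAP 4.9.3.2:

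1. Add Screening Visit 1 eGFR as a second baseline covariate beside the Visit 3 value. Do not replace the two with their mean.
2. Keep change from baseline defined on Visit 3. With Visit 3 still in the model, the treatment difference is the same whether change or the Week 12 value is analysed.
3. State that the last screening eGFR before Visit 3 is used after a retest or rescreen.
4. State how a missing Visit 3 value is handled. Under SAP 4.2 the screening value would become the baseline, so the two covariates would then coincide.
5. Record the change in SAP 4.14 as a departure from protocol 9.4.2.2, before unblinding for the final analysis.

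The cost is one model term, two sentences of definition and one entry in the list of changes. No new data are needed and the endpoint definition does not change. The single-covariate model can be kept as a supporting analysis. The fix does not by itself address the Week 12 to Week 20 change in eGFR.
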